After permanent treatment discontinuation, a safety assessment visit must be scheduled for all patients (refer to Section 5.2.3). After primary completion, follow-up information will not be collected after safety assessment visit.

Withdrawal from active follow-up

Patients *must* be withdrawn from active follow-up if any of the following occurs:

- Radiologically confirmed PD of urothelial carcinoma is observed (investigator assessment). (*Note*: this applies only to the further efficacy assessments during the active follow-up period in patients who prematurely discontinued study treatment for reasons other than radiological disease progression).
- Start of subsequent systemic anti-cancer treatment. (Note: this applies only to the further efficacy assessments during the active follow-up period in patients who prematurely discontinued study treatment for reasons other than radiological disease progression).
- At their own request or at the request of their legally acceptable representative. At any time during the study and without giving reasons, a patient may decline to participate further. The patient will not suffer any disadvantage as a result.
- Development of a malignancy other than urothelial carcinoma
- Substantial non-compliance with the requirements of the study

23 MAY 2023 Version 6.0 Page: 51 of 181

- Withdrawal of consent to active follow-up visits
- If, in the investigator's opinion, continuation of the active follow-up visits would be harmful to the patient's well-being
- Patient lost to follow-up
- Death

Withdrawal from long-term follow-up

Patients *must* be withdrawn from long-term follow-up if any of the following occurs:

- Withdrawal of consent to long-term follow-up
- Patient lost to follow-up
- Death

Patients lost to follow-up

If a patient is lost to follow-up at any stage of the study, the site will try to contact the patient, the patient's relatives, or another doctor treating the patient, unless prohibited by local requirements. All attempts to contact the patient or relatives should be documented and sites are expected to make at least 5 attempts to contact the patient over the course of 3 months. An additional contact attempt should be made at the time of the survival sweep.

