- w: After the patient has signed the informed consent for study treatment eligibility any new finding or worsening of any ongoing medical history condition must be recorded as an AE/SAE up to at least 30 days after the last administration of study treatment. In addition, any AEs after the active follow-up visit qualifying as SAEs or AESIs with an onset up to 90 days after last atezolizumab dosing that are reported to the sites need to be documented unless a new anti-cancer therapy has been initiated. Thereafter, only AEs related to the study drugs have to be recorded until the end of active follow-up. However, at the investigator's discretion, SAEs may be reported if considered potentially relevant. In such cases, the SAEs will be processed by the sponsor according to all applicable regulations.
- x: After primary completion, follow-up information will not be collected after the safety assessment visit.

23 MAY 2023 Version 6.0 Page: 93 of 181

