9.6.1.3 Assessments and documentation of adverse events

All AEs identified after the patient has signed the PI/ICF for FGFR testing and until the patient ends the study (up to at least 30 days after the last administration of study treatment) must be fully documented in the source data. AEs are obtained by observation and as volunteered by the patients. In addition, any AEs after the active follow-up visit qualifying as SAEs or AESIs with an onset up to 90 days after last atezolizumab dosing that are reported to the sites need to be documented unless a new anti-cancer therapy has been initiated.

The following procedure applies after signing of the PI/ICF for FGFR testing:

• For patients with AE or SAE related to the procedure of taking a fresh biopsy for FGFR testing the corresponding AE and SAE have to be reported in the eCRF and must be fully documented in the source data.

23 MAY 2023 Version 6.0 Page: 122 of 181

• For all other events, these have to be fully documented in the source data and will be reported in the medical history only for those patients who have signed the PI/ICF for study treatment eligibility.

The following procedure applies after signing of the PI/ICF for study treatment eligibility.

- For screening failures, the investigator must record every SAE (see Section 11.1) and AE in the eCRF from the PI/ICF until date of screening failure.
- For patients eligible for treatment, all AEs and SAEs identified from the PI/ICF up to at least 30 days after the last administration of study treatment must be reported on the eCRF. Thereafter, only AEs related to the study drugs have to be recorded until the end of active follow-up. In addition, any AEs after the active follow-up visit qualifying as SAEs or AESIs with an onset up to 90 days after last atezolizumab dosing that are reported to the sites need to be documented unless a new anti-cancer therapy has been initiated.

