After the end of the active follow-up phase, there is no requirement to actively collect AEs (deaths will continue to be followed for efficacy purposes up to primary completion). An AE (irrespective of causal relationship) not completely resolved at the end of the pre-defined collection period must be followed up until resolution (chronicity, baseline grade or complete resolution) or until the investigator considers the event will not improve further. The type of information that should be assessed and recorded by the investigator for each AE is listed in Section 9.6.1.2.

The investigator is responsible for grading and judging the causal relationship (see Section 9.6.1.2.3) of the recorded AEs.

AE documentation is event-based: All AEs that were ongoing at the end of treatment should be reviewed and updated up to at least 30 days after the last administration of study treatment. All new AEs that in the opinion of the investigator could be related to study treatment (information may be obtained via phone call), should also be collected and recorded up to at least 30 days after the last administration of study treatment. In addition, any AEs after the active follow-up visit qualifying as SAEs or AESIs of atezolizumab with an onset up to 90 days after last atezolizumab dosing that are reported to the sites need to be documented unless a new anti-cancer therapy has been initiated.

All AEs should be followed until resolution or stabilization unless, in the investigator's opinion, the condition is unlikely to resolve due to the patient's underlying disease. If any patient should die within 30 days of discontinuation of rogaratinib treatment or within 90 days of discontinuation of atezolizumab treatment, the investigator will inform the sponsor and record the cause of death in detail within 24 hours of awareness on an SAE form.

Documentation must be supported by an entry in the patient's file. A laboratory test abnormality considered clinically relevant, e.g. causing the patient to withdraw from the study, causing dose modification of the study treatment, requiring treatment or causing apparent clinical manifestations, or judged relevant by the investigator, should be reported as an AE.

23 MAY 2023 Version 6.0 Page: 123 of 181

"Death" should not be recorded as an AE on the AE page. Instead, "death" is the outcome of underlying AE(s).

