6.4.2 Adverse Events (AEs)

Individual listings of AEs will be provided. AEs will be reported using MedDRA terms (version 20.0 or later) and graded according to NCI CTCAE version 4.03.

AEs will be considered to be treatment-emergent if they have started or worsened after first administration of study drug up to 30 days after the last dose of rogaratinib or 90 days after the last atezolizumab administration, whichever comes later.

The incidence of treatment-emergent adverse events (TEAEs), drug-related adverse events (TEADRs), treatment-emergent and drug-related serious adverse events (SAEs), respectively, will be summarized by MedDRA system organ class and worst NCI-CTCAE grade. TEAEs, SAEs, TEADRs, and drug-related SAEs for events of Grade 3/4/5 will be summarized similarly.

Subject listings of all AEs, SAEs, AESI, TEAEs leading to dose reduction, TEAEs leading to dose interruption, TEAEs leading to discontinuation, AEs leading to DLTs and deaths will be presented. For death, two listings (“during treatment and within 30 days post permanent treatment discontinuation” and “after 30 days post permanent treatment discontinuation”) will be provided.

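### All-cause TEAE incidence is counted to 90 days after atezolizumab, but all AEs must be recorded only to at least 30 days after the last study treatment, so it is a lower bound for its stated window

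*SAP*

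**What the plan says.** **What is counted.** Protocol 5.3 makes the incidence of TEAEs, drug-related TEAEs and treatment-emergent SAEs a primary variable. SAP 6.4.2 and protocol 10.3.4.2 count events that start or worsen after the first dose "up to 30 days after the last dose of rogaratinib or 90 days after the last atezolizumab administration, whichever comes later". Protocol 9.6.1.1 gives the same two limits without saying which prevails; the other two sections settle that.

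**What is collected.** Protocol 9.6.1.3 requires all AEs and SAEs "up to at least 30 days after the last administration of study treatment must be reported on the eCRF". Footnote w to Table 9–2 repeats the rule: a new or worsened condition "must be recorded as an AE/SAE up to at least 30 days after the last administration of study treatment". Collection then narrows in two ways:
- "Thereafter, only AEs related to the study drugs have to be recorded until the end of active follow-up".
- SAEs and AESIs with onset up to 90 days after atezolizumab are kept only if they are events "that are reported to the sites need to be documented unless a new anti-cancer therapy has been initiated".

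Two safeguards apply. "An AE (irrespective of causal relationship) not completely resolved at the end of the pre-defined collection period must be followed up until resolution". And if a patient dies within 30 days of stopping rogaratinib or "within 90 days of discontinuation of atezolizumab treatment, the investigator will inform the sponsor and record the cause of death".

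**What is tabulated.** SAP 6.4.2 plans TEAE, drug-related and SAE tables by system organ class and worst grade, plus Grade 3/4/5 versions. None is limited to the period in which all AEs must be recorded. Only the death listings are split at 30 days.

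**The concern.** The all-cause TEAE tables join two periods under one label: one in which every AE must be recorded, and a later one in which recording depends on causality, seriousness, AESI status, what reaches the site and whether new therapy has begun. A reader will take the percentages as complete incidence to 90 days after atezolizumab. They are not, and no planned table shows the incidence over a period that was fully observed. Safety is the primary objective of Part A, so the label on these tables matters.

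**Working it through.** The plan states no figure for this gap, so there is none to reproduce. The check compares two windows in days.

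**Inputs**
- End of the TEAE window: the later of last rogaratinib + 30 and last atezolizumab + 90 days (SAP 6.4.2).
- Minimum end of all-AE collection: last study treatment + 30 days (protocol 9.6.1.3). Study treatment means both drugs (protocol 7.2), so the 30 days run from whichever stops later.
- Safety visit: day 30, up to +7 (protocol 5.2.3). Let v be the last day of full collection after the last dose, so v = 30 to 37.
- Atezolizumab is given on Day 1 and rogaratinib on all 21 days of a cycle (protocol 7.4.1). Let g be the days by which rogaratinib outlasts atezolizumab, with g = 0 if rogaratinib stops first. Stopping both in the same cycle gives g = 0 to 20 (21 − 1).

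**Formula**, in days from the last atezolizumab dose
- Window end = max(90, g + 30).
- Full collection ends at g + v.
- Partly covered days = max(0, 90 − g − v). Once g + 30 reaches 90, full collection lasts at least as long as the window.

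**Results**

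| g | v = 30 | v = 37 |
|---|---|---|
| 0 | 90 − 0 − 30 = 60 | 90 − 0 − 37 = 53 |
| 20 | 90 − 20 − 30 = 40 | 90 − 20 − 37 = 33 |
| 42 | 90 − 42 − 30 = 18 | 90 − 42 − 37 = 11 |
| 60 | 0 | 0 |

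At v = 37 the gap already closes at g = 53. Where treatment ends after an interruption of more than 30 days, the visit can fall later. Assuming a 31-day interruption and a visit 14 days after it, v = 45 and the same-cycle range is 25 to 45 days. For a table cut at last study treatment + 30 days, the window ends at g + 30 and collection at g + v, so with v of at least 30 the gap is 0 for every patient.

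**What the partly covered days contain**

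| Event | Requirement |
|---|---|
| New, unrelated, non-serious, not an AESI | None |
| SAE or AESI | Documented if reported to the site, until new anti-cancer therapy |
| Drug-related AE | Recorded to the end of active follow-up |
| AE unresolved when collection ends | Followed to resolution, whatever its cause |
| Death within 90 days of stopping atezolizumab | Must be reported |

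**Direction.** An event that meets the TEAE definition but need not be recorded can only lower the count. The 30 days are a minimum, so sites may record more, perhaps unevenly, but the recorded incidence cannot exceed the true incidence in the window.

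**Late drug-related AEs.** Protocol 9.6.1.3 and footnote w require them to the end of active follow-up without naming a subgroup. Protocol 5.2.3 and footnote b to Figure 5–1 describe continued collection for patients who stopped without radiological progression. The notes in 6.4.1.3 on leaving active follow-up for progression or new therapy say "this applies only to the further efficacy assessments during the active follow-up period", but each sentence goes on to limit itself to patients who stopped for reasons other than radiological progression. They do not establish continued safety follow-up for everyone.

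**The case against.** **The tiering is deliberate and the important events are covered.** The amendment log gives avoidance of unnecessary reporting as a reason for limiting 90-day reporting to SAEs and AESIs. The AESI list in protocol 9.6.1.6 is broad, unresolved AEs are followed, and deaths must be reported. This stands, and it confines the loss mainly to late, unrelated, non-serious, non-AESI events. It does not align the counting window with the collection.

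**Nothing turns on these rates.** Part A is single-arm and descriptive. No decision rule uses all-cause TEAE incidence, and the synopsis time frame for TEAEs, though broken in the text, refers to all cycles. This stands for dose finding. But SAP 6.4.2 plans no by-cycle or on-treatment TEAE table, so the reported rate is the one over the long window.

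**A footnote would do.** It would correct the label, but would still give the reader no incidence over a fully observed period.

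**Two stronger readings should be resisted.**
- A reader might take 60 of the 90 days after atezolizumab to mean that two thirds of late events are lost. The tables count patients by worst grade, so a patient who already had the same event at an equal or worse grade adds nothing later. Much of what occurs late is still collected, and the documents give no late AE rates.
- A reader might also see a proven contradiction on late drug-related AEs. The sections can be read together if active follow-up ends at the safety visit for patients who progressed, so this is an ambiguity.

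**Conclusion.** The point holds as a matter of interpretation and labelling. All-cause TEAE incidence is a lower bound for the window in SAP 6.4.2. Treatment-emergent SAEs may be affected to a lesser degree, because late ones rely on reports to the site and stop at new therapy. Late drug-related AEs may be too, depending on which patients remained in active follow-up.

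The size can be given only in days: 40 to 60 at the 30-day minimum and 33 to 53 with a day-37 visit, for patients who stop both drugs in the same cycle. It shrinks as rogaratinib outlasts atezolizumab and is zero from 60 days. This assumes that full collection ends at the minimum or at the safety visit. The number of patients or events missed cannot be estimated from the documents. Cycle 1 DLT and MTD results do not depend on this window.

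**What to change.** Keep the pre-specified window and every existing table. In SAP 6.4.2 add:

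1. All-cause TEAE and Grade 3/4/5 TEAE tables limited to onset or worsening up to 30 days after the last dose of study treatment (the later of the two drugs), labelled as the fully collected period.
2. One table of all AEs recorded after that point to the end of the TEAE window, whatever their type, labelled as selectively collected, with events after new anti-cancer therapy flagged. Including every type keeps unrelated, non-serious AEs noted between day 30 and the safety visit from falling outside both new displays.
3. A footnote on the existing TEAE tables stating the collection rules.

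Also clarify whether late drug-related AEs are collected for all patients or only for those who stopped without radiological progression (protocol 5.2.3 and Figure 5–1 against 9.6.1.3 and Table 9–2), and state the rule applied in that footnote.

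The cost is three tables built from dates already recorded, a footnote and a clarification. No recorded event is dropped. The downside is two windows to explain in the report.

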6.4.3 Clinical Laboratory Data

The incidence of laboratory data outside the reference range (low, high) will be summarized in frequency tables. The incidence of hematological and biochemical laboratory values will be summarized by worst NCI CTCAE version 4.03 grade. Frequency tables will be provided for the changes of worst NCI CTCAE version 4.03 grade after start of treatment versus baseline and under treatment Descriptive statistics (number of observations, mean, standard deviation, minimum, median and maximum values) will be presented for clinical laboratory tests (hematology, general chemistry and coagulation), their changes from baseline (including baseline value). Mean and standard deviation will be graphically displayed as well.. The number of subjects with urinalysis results will be tabulated by visit. Subjects will also be presented subdivided into classes according to their calcium phosphate product lower than 70 mg^2/dL^2 and equal to or higher than 70 mg^2/dL^2 .

6.4.4 COVID-19 additional analysis

Due to the global pandemic, listings of all COVID-19 related important PDs, COVID-19 related study disruptions and subjects with COVID-19 related AEs will be provided.

6.4.5 Other Safety Data

Quantitative data (such as vital signs, electrocardiogram) will be described by the following summary statistics: arithmetic mean, standard deviation, median, minimum and maximum. These summary statistics will be presented for the original data as well as for the difference to baseline. Frequency tables will be provided for qualitative data, such as ECG findings and interpretation.

The average of triplicate quantitative ECG parameters at all ECG time points will be used for all analyses.

ECOG performance status will be summarized by visit for observed values and changes from baseline using summary statistics. Ophthalmologic interpretation will be tabulated in frequency tables.

Number of women taking a pregnancy test and the result will be tabulated by visit.

7. Document history and changes in the planned statistical analysis

- SAP, Version 1.0, 19 JUN 2018

- SAP Amendment, 02 APR 2020
 - Wording was harmonized throughout the document;
 - Added wording changes from protocol amendment 2;
 - Added definitions for pre-screening failures and screening failures;
 - Added information on the validity review meeting;
 - Clarified that only subjects from the dose selection part are to be considered for the MTD analysis set;
 - Planned analysis for prior immunotherapy, duration of treatment, TTP, dose modifications;
 - Added plan for the biomarker/pharmacodynamics analysis.
- SAP Amendment, 05 OCT 2021
 - PK concentration data of only rogaratinib (previously also atezolizumab) will be tabulated in Cycle 1
 - Addition of TTR definition
 - Addition of Covid-19 analyses
 - Wording change: patient replaced by subject
 - Specification of CSP reference: Section 7.4.3
- SAP Supplement, 05 APR 2022
 - Section 2: Addition of wording about part B not being conducted
 - Section 6.1.1: Addition of presentation of countries and study centers
 - Section 6.1.2: Deletion of NYHA in demographic variables
 - Section 6.1.2: Deletion of status of primary tumor and clinical status at study entry in cancer baseline characteristics
 - Section 6.1.3: Addition of wording about therapies during follow-up
 - Section 6.2.3: Addition of Follow-up time definition and more detailed wording
 - Section 6.2.4: Addition of visits of the summary statistics of EORTC QLQ-C30 and the analysis set
 - Section 6.4.2: Deletion of frequency tables for change of CTCAE grade from pre-treatment
 - Section 6.4.3: Deletion of listing of laboratory data outside the reference range with abnormal values flagged
 - Section 6.4.3: Addition of more details about clinical laboratory data analysis
 - Section 6.4.5: Addition of more details about other safety data

8. References

[1] Clinical Study Protocol No. BAY 1163877 / 19131, version 4.0, 04 Oct 2021
